CLINICAL TRIAL PROTOCOL

PLN-74809-IPF-205

Study Title: A Phase 2a, randomized, double-blind, placebo-controlled evaluation of PLN-74809 on type 1 collagen deposition using ⁶⁸Ga-CBP8 PET/MRI imaging in participants with idiopathic pulmonary fibrosis (IPF)

Study Number: PLN-74809-IPF-205

Study Phase: 2a

Product Name: PLN-74809-000

IND Number: 139,998

Indication: Treatment of idiopathic pulmonary fibrosis (IPF)

Sponsor: Pliant Therapeutics Inc.
[name]
[name]

Sponsor Study Director: [REDACTED]
Pliant Therapeutics Inc.
[REDACTED]

	Date
Original Protocol (v1.0):	22 June 2021
Amendment 1:	4 October 2021

Confidentiality Statement

This document is the property of Pliant Therapeutics. The confidential information in this document may not be used, published or disclosed without the prior written consent of Pliant Therapeutics except to the extent required under applicable laws or regulations.

SYNOPSIS

Study Title:	A Phase 2a, randomized, double-blind, placebo-controlled evaluation of PLN-74809 on type 1 collagen deposition using ⁶⁸ Ga-CBP8 PET/MRI imaging in participants with idiopathic pulmonary fibrosis (IPF)
Study Number:	PLN-74809-IPF-205
Study Phase:	2a
Number of Participants	Approx. 12 (8 receiving PLN-74809 and 4 receiving placebo)
Objectives:	
Primary:
 
 Quantification of type 1 collagen in the lung following 12 weeks of treatment with PLN-74809, as assessed by changes from Baseline in ⁶⁸Ga-CBP8 positron emission tomography (PET) / magnetic resonance imaging (MRI) tracer uptake patterns 
Secondary:
 
 Assessment of the safety and tolerability of PLN-74809 in idiopathic pulmonary fibrosis (IPF) participants 
Exploratory:
 
 Relationship between PLN-74809 systemic exposure and PET imaging and biomarkers in IPF participants Forced vital capacity (FVC): absolute FVC volume and FVC as percent of predicted as assessed by spirometry Patient-reported outcome (PRO): a visual analog scale (VAS) for cough severity
Study Design:	
This is a Phase 2a, single-center, randomized, double-blinded, placebo-controlled study to evaluate type 1 collagen deposition in the lungs following once-daily (QD) treatment with 160 mg PLN-74809 for 12 weeks in participants with IPF.
 
The study consists of an up to 28-day screening period, a 12-week treatment period, and a 2 week (± 3 days) post treatment follow-up period.
 
Potential participants who provide written informed consent will be screened for study eligibility up to 28 days before administration of the first dose of study drug.
 
Approximately 12 eligible participants will be randomized in a 2:1 ratio (160 mg PLN-74809 vs placebo; 8 receiving PLN-74809 and 4 receiving placebo) on Day 1 (Visit 3). Study treatment will be administered once daily for 12 weeks.
 
Randomization will be stratified by use of standard of care (SoC) IPF therapy with pirfenidone or nintedanib (SoC use; yes or no).
 
⁶⁸Ga-CBP8 PET/MRI scans will be conducted within 7 days prior to baseline and at or within 7 days prior to Week 12, as indicated in the Schedule of Events.
 
Participants who discontinue study drug for safety reasons prior to completion of 12 weeks of treatment will be encouraged to remain in the study to complete all remaining assessments; if this is not feasible, they will be asked to return to the clinic for an Early Termination (ET) visit for follow-up evaluations. If a participant elects to withdraw from the study after the 6th week of randomization, an end of participation ⁶⁸Ga-CBP8 PET/MRI will be offered to the participant to enhance appropriate data capture.
 
Potential acute exacerbations, respiratory-related hospitalizations, and/or respiratory-related deaths will be reviewed by an adjudication committee.

Study Population:	
Inclusion Criteria:
 
 1. Participants, aged 40 years or older 2. Diagnosis of IPF, within 8 years prior to screening, according to the American Thoracic Society (ATS)/ European Respiratory Society (ERS)/ Japanese Respiratory Society (JRS)/ Latin American Respiratory Society (ALAT) 2018 guidelines Note: If IPF diagnosis is within > 3 to ≤ 8 years at screening, the participant must have evidence of progression within the last 24 months, as defined by decline in FVC percent predicted based on a relative decline of ≥ 5% 3. FVC percent of predicted ≥ 45%; historical FVC for entry in the study is permitted if within 1 month of screening 4. Diffusing capacity for carbon monoxide (DLco) (hemoglobin-adjusted) ≥ 30%; historical DLco for entry in the study is permitted if within 1 month of screening 5. Participants currently receiving treatment for IPF with nintedanib or pirfenidone are allowed, provided these drugs have been given at a stable dose for at least 3 months before the Screening Visit and are expected to remain unchanged during the study (stable dose is defined as the highest dose tolerated by the participant during ≥ 3 months) 6. Estimated glomerular filtration rate ≥ 50 mL/min, according to the Cockcroft-Gault equation 7. Female participants of non-childbearing potential must be either surgically sterile or postmenopausal 8. Female participants of childbearing potential must use a contraceptive method with a failure rate of <1% per year or remain abstinent (refrain from heterosexual intercourse) during the treatment period and for 1 month after the last dose of study treatment 9. Male participants with female partners of childbearing potential must agree to use contraceptive measures or remain abstinent (refrain from heterosexual intercourse) during the treatment period and for at least 3 months after the last dose of study treatment. 10. Participants must agree to abstain from sperm or egg donation for the duration of the study, through to 3 months or 1 month, respectively, after administration of the last dose of study drug 11. Able to understand the purpose of the study and its procedures and to sign a written informed consent form (ICF) 
Exclusion Criteria:
 
 1. Hypersensitivity to PLN-74809 or to any of the excipients to PLN-74809 2. Not a suitable candidate or unlikely to comply with study requirements, in the opinion of the Investigator 3. Receiving any nonapproved agent intended for treatment of fibrosis in IPF 4. Forced expiratory volume during the first seconds of the forced breath (FEV1)/FVC ratio < 0.7 at screening 5. Clinical evidence of active infection, including but not limited to bronchitis, pneumonia or sinusitis that can affect FVC measurement during screening or at randomization 6. Any other condition that prevents the correct assessment of spirometry performance (e.g., a broken rib or chest pain of other origin that prevents adequate forced breathing) 7. Known acute IPF exacerbation or suspicion by the Investigator of such, within 6 months of screening
--------------------------	--

	
 8. Severe pulmonary hypertension 9. Smoking of any kind (not limited to tobacco) within 3 months prior to screening, as documented in the medical history, or unwilling to avoid smoking throughout the study 10. Lower respiratory tract infection requiring antibiotics within 4 weeks prior to screening and/or during the screening period 11. History of malignancy within the past 5 years or ongoing malignancy other than basal cell carcinoma, resected noninvasive cutaneous squamous cell carcinoma, or treated cervical carcinoma in situ 12. End-stage liver disease 13. Renal impairment or end-stage kidney disease requiring dialysis 14. History of unstable or deteriorating cardiac or pulmonary disease (other than IPF) within the 6 months prior to screening, including but not limited to the following: 
 a. Unstable angina pectoris or myocardial infarction b. Congestive heart failure requiring hospitalization c. Uncontrolled clinically significant arrhythmias (e.g., resulted in health care utilization or hospitalization) 15. Any clinically relevant electrocardiogram (ECG) abnormalities, including but not limited to, QT interval corrected for heart rate using Fridericia's formula (QTcF) > 450 msec for males or > 460 msec for females at the Screening Visit (including Day -1) or prior to administration of the initial dose of study drug 16. Any medical condition that, in the opinion of the Investigator, may make the candidate not suitable for the study 17. History of anaphylaxis to intravenous (IV) drugs 18. Any of the following liver function test criteria above specified limits: total bilirubin $> 1.5 \times$ the upper limit of normal (ULN); aspartate aminotransferase (AST) or alanine aminotransferase (ALT) $> 3 \times$ ULN; alkaline phosphatase $> 2.5 \times$ ULN. Note: participants currently receiving nintedanib or pirfenidone as IPF SoC treatment, who have previously presented any liver function test elevations associated with nintedanib or pirfenidone treatment greater than that described above or resulting in dose reduction, treatment interruption, or discontinuation are not eligible. 19. Any of the following at screening: hemoglobin < 10.0 g/dL, neutrophils < 1500 /mm³, or platelets $< 100,000$ /mL 20. Electrical implants such as cardiac pacemaker or perfusion pump 21. Ferromagnetic implants such as aneurysm clips, surgical clips, prostheses, artificial hearts, valves with steel parts, metal fragments, shrapnel, metallic tattoos anywhere on the body, tattoos near the eye, or steel implants, ferromagnetic objects such as jewelry or metal clips in clothing 22. Claustrophobic reactions 23. Research-related radiation exposure exceeds current Radiology Department guidelines (i.e. 50 mSv in the prior 12 months) 24. Unable to lie comfortably on a bed inside the PET/MRI 25. Body mass index (BMI) > 33 kg/m² (limit of the PET/MRI table) 26. Prior or current radiation to the thorax 27. Pregnant or lactating female participants 28. Male participants with pregnant female partners 29. A medical or surgical condition known to affect drug absorption (e.g., major
--	--

	
gastric surgery)
 
30. Participation in a clinical study with an investigational agent in the 30 days prior to screening or 5 half-lives of the investigational drug, whichever is longer trial, apart from PLN-74809
 
31. Currently receiving and expected to remain on treatment during the study with: potent and concomitant inhibitors or inducers of cytochrome P450 (CYP) 3A4, 2C9 or 2C19; potent inhibitors or inducers of P-glycoprotein (P-gp), breast cancer resistance protein (BCRP) or organic anion transporting polypeptide (OATP) 1B1/1B3 transporters; digoxin (a P-gp substrate with a narrow therapeutic window)
 
32. Daily use of phosphodiesterase-5 (PDE-5) inhibitor drugs (e.g., sildenafil, tadalafil, other) (Note: Intermittent use for erectile dysfunction is allowed.)
 
33. Surgical procedures planned to occur during the study period
 
34. Uncontrolled systemic arterial hypertension
 
35. Likely to have lung transplantation during the study (being on transplantation list is acceptable)

Test Product, Dose, and Mode of Administration:	PLN-74809 (80 mg immediate release tablets) 160 mg, oral, QD
Reference Therapy, Dose, and Mode of Administration:	Matching placebo - Oral, QD
PET Tracer, Dose, and Mode of Administration:	The ⁶⁸ Ga-CBP8 PET/MRI tracer is not considered a study treatment but is an investigational tool used during the PET procedure for obtaining the images necessary for this trial. [68Ga]CBP8 is an intravenous injection given within 7 days prior to baseline and at or within 7 days prior to Week 12. The radiochemical dose is up to 12.9 mCi but in practice, the dose has averaged 5.5 mCi per subject.
Duration of Treatment:	12 weeks
Pharmacokinetic and Pharmacodynamic Assessments	
Pharmacokinetic Assessments
 
On Day 1, total and unbound plasma samples for PLN-74809 pharmacokinetic (PK) analysis will be obtained predose and at 2, 4, and 6 hours postdose. At steady-state, total and unbound plasma samples for PLN-74809 PK analysis will be obtained predose and at least 2 hours postdose at Weeks 4 and 12.
 
Pharmacodynamic Assessments
 
PET/MRI Imaging for the Assessment of Type 1 Collagen Deposition
 
All PET/MRI will be performed at the Martinos Center for Biomedical Imaging at Massachusetts General Hospital. PET imaging will be performed at prespecified times as indicated in the Schedule of Events. Blood samples will be obtained prior to each PET/MRI and will be stored for future analyses. The total amount of radiation exposure from the PET/MRI is equal to a whole-body exposure up to 22 mSv (11 mSv per administration of ⁶⁸GaCBP8).
 
MRI for the Assessment of PET/MRI Relationship
 
All participants will undergo dynamic contrast-enhanced MRI during each PET/MRI session. This will be performed using gadoterate meglumine at a predefined weight-base dose and injection rate, as detailed in the study's Radiology Manual.
 
Biomarkers in Urine, Plasma, and Serum
 
Urine, plasma and serum samples will be obtained at predetermined times as indicated in the Schedule of Events. These samples will be used to measure specific proteins, peptides, metabolites and/or messenger ribonucleic acid (mRNA) transcripts that may

	
be elevated in patients with inflammatory/fibrotic disease or act as pharmacodynamic (PD) markers that may change with inhibition of $\alpha_v\beta_6$.
 
Pharmacogenomic Assessments
 
A whole blood sample for deoxyribonucleic acid (DNA) isolation will be collected before dosing on Day 1 from each participant in the study.

Exploratory Efficacy Assessments:	
Spirometry
 
Absolute FVC volume and FVC percent of predicted will be assessed by spirometry at screening and at the timepoints specified in the Schedule of Events. FEV1 will be assessed by spirometry at screening.
 
Patient-reported Outcome (PRO)
 
Study participants will respond to a VAS for cough severity at the timepoints specified in the Schedule of Events.

Safety Assessments:	Open ended adverse event (AE) inquiry; clinical chemistry and hematology; vital signs; 12-lead ECG
Sample Size Justification:	The sample size of approximately 12 participants (8 participants receiving 160 mg PLN-74809 and 4 receiving placebo) is expected to provide a meaningful evaluation of PLN-74809 safety, tolerability and PK in the target population, and add to the data of approximately 21 participants planned to be evaluated at this dose level in an ongoing multicenter, dose ranging Phase 2a study (PLN-74809-IPF-202).
Statistical Methods:	
Analysis Populations
 
Safety Population: All randomized participants who receive at least one dose of study drug will be included in the safety analyses.
 
PK Analysis Population: All randomized participants who have sufficient PLN-74809 concentration data for PK calculation will be included in the PK analyses.
 
PD Analysis Population: All randomized participants who receive any amount of study drug and who have results from Baseline and from at least one post-baseline PET/MRI scan or PD assessment will be included in the PD analyses.
 
Primary Endpoint: PD
 
Quantification of type 1 collagen in the lung following 12 weeks of treatment, as assessed by changes from Baseline in ^{68}Ga-CBP8 PET/MRI tracer uptake patterns.
 
PET/MRI scans will be interpreted by American Board of Nuclear Medicine (ABNM)-certified nuclear medicine physicians in an unblinded manner. Lung contours will be generated from baseline and post-treatment PET/MRI. Mean and maximum standardized uptake value (SUV) measurements of contoured lungs will be calculated using MIMS software, by analyzing the uptake values of ^{68}Ga-CBP8 PET/MRI within the lung, and by comparing values from the baseline and post-treatment scans. Numerical and graphical results will be presented by dose.
 
In addition, relationships between PK and type 1 collagen deposition, as well as between MRI and PET imaging, may be evaluated in an exploratory fashion and presented in a graphical manner
 
Secondary Endpoint: Safety
 
Safety data from all participants who received at least one dose of study drug will be incorporated into the final safety analysis.
 
Exploratory Endpoints
 
PK and PD
 
Plasma PLN-74809-versus-time profiles (with plasma concentrations on both a log and linear scale) will be plotted for each participant. Non-compartmental analysis will be used to calculate PK parameters as appropriate.
 
Relationships between PK and type 1 collagen deposition, as well as between MRI and PET imaging, may be evaluated in an exploratory fashion and presented in a graphical manner.

	
Urine, plasma, and serum samples will be analyzed for biomarkers (presence or actual concentration). These samples will be used to determine the levels of these markers in participants, the relationship between these markers, and the level of PET tracer uptake (type 1 collagen deposition) in the lung.
 
Efficacy
 
Percent of predicted FVC and volume will be assessed using the standard spirometry procedure at the Chest Clinic at Massachusetts General Hospital and presented as absolute values and as percent of predicted values. Baseline FVC will be the average of the screening and Day 1 determinations. End-of-study FVC will be the average of Week 12 and Week 14 determinations.
 
For PRO, cough VAS will be completed at the timepoints specified in the Schedule of Events.

--	---

TABLE OF CONTENTS

CLINICAL TRIAL PROTOCOL	1
PLN-74809-IPF-205.....	1
SYNOPSIS.....	2
TABLE OF CONTENTS	8
LIST OF IN-TEXT TABLES	11
LIST OF APPENDICES	11
LIST OF ABBREVIATIONS.....	12
1 INTRODUCTION	15
1.1 Summary of Clinical Development.....	15
1.1.1 Completed Phase 1 Studies	15
1.1.2 Ongoing Phase 1 Study PLN-74809-104.....	16
1.1.3 Ongoing Phase 2 studies	16
1.2 Study Rationale for PLN-74809-IPF-205	17
2 STUDY OBJECTIVES.....	19
2.1 Primary Objective	19
2.2 Secondary Objectives	19
2.3 Exploratory Objectives.....	19
3 INVESTIGATIONAL PLAN.....	20
3.1 Overall Study Design and Plan	20
3.2 Rationale for PLN-74809 Doses and Control Group.....	20
3.3 Study Duration.....	21
4 STUDY POPULATION SELECTION.....	22
4.1 Study Population.....	22
4.2 Inclusion Criteria.....	22
4.3 Exclusion Criteria.....	23
5 STUDY DRUG AND ACCOUNTABILITY	26
5.1 Description of Study Drug.....	26
5.1.1 Study Drug	26
5.1.2 Placebo	26
5.1.3 PET Tracer	26
5.2 Packaging and Labeling	26
5.3 Storage and Accountability.....	26
5.4 Treatment Compliance	26
6 STUDY TREATMENTS	28
6.1 Description of Treatments	28
6.2 Dose Modifications and Interruptions.....	28
6.3 Selection and Timing of Dose for Each Participant.....	28

6.4	Method of Assigning Participants to Treatment Groups.....	29
6.5	Blinding	29
6.6	Concomitant Therapy	29
6.6.1	Allowed Medications.....	29
6.6.2	Disallowed Medications.....	30
6.7	Restrictions	31
6.7.1	Prior Therapy.....	31
6.7.2	Fluid and Food Intake	31
6.7.3	Participant Activity Restrictions.....	31
6.7.4	Contraception	31
7	STUDY PROCEDURES.....	33
7.1	Informed Consent.....	33
7.2	Medical History.....	33
7.3	Demographic Information	33
7.4	Physical Examination	33

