3 INVESTIGATIONAL PLAN

3.1 Overall Study Design and Plan

This is a Phase 2a, single-center, randomized, double-blinded, placebo-controlled study to evaluate type 1 collagen deposition in the lungs following once-daily (QD) treatment with 160 mg PLN-74809 for 12 weeks in participants with IPF.

The study consists of an up to 28-day screening period, a 12-week treatment period, and a 2-week (± 3 days) post treatment follow-up period.

Potential participants who provide written informed consent will be screened for study eligibility up to 28 days before administration of the first dose of study drug. Approximately 12 eligible participants will be randomized in a 2:1 ratio (160 mg PLN-74809 vs placebo; 8 receiving PLN-74809 and 4 receiving placebo) on Day 1 (Visit 3). Study treatment will be administered once daily for 12 weeks. Randomization will be stratified by use of standard of care (SoC) IPF therapy with pirfenidone or nintedanib (SoC use; yes or no).

^{68}Ga -CBP8 PET/MRI scans will be conducted within 7 days prior to baseline and at or within 7 days prior to Week 12, as indicated in the Schedule of Events ([Appendix 1](#)).

Participants who discontinue study drug for safety reasons prior to completion of 12 weeks of treatment will be encouraged to remain in the study to complete all remaining assessments; if this is not feasible, they will be asked to return to the clinic for an Early Termination (ET) visit for follow-up evaluations. If a participant elects to withdraw from the study after the 6th week of randomization, an end of participation ^{68}Ga -CBP8 PET/MRI will be offered to the participant to enhance appropriate data capture.

Potential acute exacerbations, respiratory-related hospitalizations, and/or respiratory-related deaths will be reviewed by an adjudication committee.

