8.8.3 Reporting Serious Adverse Events

In order to meet the requirements for expedited reporting of SAEs meeting specific requirements to applicable regulatory authorities and Institutional Review Boards (IRBs)/ Independent Ethics Committee (IECs)/ Research Ethics Boards (REBs), all SAEs must be reported to the Sponsor per the Study Manual within 24 hours from the time site personnel first become aware of the event by completing the SAE form and emailing it to the below:

[contact]

Initial notification of an SAE by telephone must be confirmed in writing within 24 hours by completing the SAE form. As further information regarding the SAE becomes available, such follow up information should be documented and sent to ***[contact]***.

All SAEs must be followed by the Investigator to resolution or medical stabilization.

Withdrawal from the study in the event of a SAE and therapeutic measures taken shall be at the discretion of the Investigator. A full explanation for the discontinuation from the study should be made in the eCRF.

8.8.4 *Reporting SAEs to Regulatory Authorities and IRB/IEC/REB*

The reporting of any SAEs to applicable regulatory authorities will be the responsibility of the Sponsor in compliance with applicable country regulations. All SAEs must be reported to the IRB/IEC/REB by the Investigator in accordance with their regulations.

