Any participant who experiences a QTc prolongation not confirmed upon repeat ECG assessment may continue or resume administration of study drug and follow the scheduled study visits, if clinically appropriate. More frequent clinical evaluation and ECG monitoring through use of unscheduled visits is allowed, if clinically warranted.

Participants who permanently discontinue study drug due to potential QTc prolongation must be followed for close monitoring until abnormalities stabilize to baseline levels or baseline grade of abnormality and the participant is asymptomatic. Participants should be encouraged to remain in the study and completed all scheduled visits and assessments. Long-term follow-up information should be provided for participants who permanently discontinue drug due to confirmed QTc prolongation, including information on corrective therapy and cardiology consultation, if applicable.

11 **EARLY DISCONTINUATION OF STUDY OR INDIVIDUAL PARTICIPANTS**

In accordance with the Declaration of Helsinki, participants have the right to withdraw from the study at any time for any reason. The Investigator or Sponsor may withdraw a participant from the study or discontinue study drug for any of the following reasons:

- Noncompliance with protocol procedures including those relating to administration of study drug
- A serious or intolerable AE occurs
- Infection with COVID-19 that precludes safe participation in the study
- A clinically significant change in a laboratory parameter occurs
- Confirmed elevations in serum ALT or AST meeting criteria for suspected acute DILI (see [Section 9](#))
- Prolonged ECG QTc interval meeting criteria for permanent discontinuation (see [Section 10](#))
- Male participants whose female partners become pregnant during the study must stop the medication immediately
- The Sponsor or Investigator terminates the study
- The participant requests to be discontinued from the study

If a participant is withdrawn from the study or discontinues study drug, they will undergo early termination assessments; refer to the Schedule of Events ([Appendix 1](#)).

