5.2.7 Early Terminations Assessments

Early Termination (ET) assessments will not be summarized unless the ET visit falls on a scheduled visit. ET assessments will be listed only.

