5.11.1 Primary Endpoint

The primary endpoint is the change from baseline to week 12 in the top quartile mean SUV for the whole lung (average of the right and left lungs).

Whole lung and by lung region top quartile SUVs will be summarized using descriptive statistics by treatment groups and visit for the PD Population.

In addition, an analysis of covariance (ANCOVA) model will be used to summarize the primary endpoint. The model will include terms for baseline top quartile mean SUV and treatment group. The LS means, corresponding SEs, and 95% CI for each treatment group will be obtained from the model. An estimate for the LS mean difference (PLN-74809 vs. placebo), corresponding SE, 95% CI, and *P*-value for each dose group will also be presented.

Example [REDACTED] for ANCOVA model is provided below, [REDACTED] may be added or adjusted for ease of output and interpretation:

[REDACTED]

Where

base	is value at baseline
chg	is change of from baseline
socyn	is the participant's use of standard of care at baseline (Yes or No)
trt	is the dose group

Whole lung and by region metric SUVs will be presented as a box plots by treatment group (side-by-side) with all regions on the same figure.

QMD Ref: [REDACTED]	Governing QMD: [REDACTED]
Confidentiality Statement	
This document is the property of [REDACTED] without prior approval from [REDACTED]	and may not be duplicated, copied, altered or removed from company or in compliance with [REDACTED]
REF: [REDACTED]	

		Controlled Quality Management Document
		Sponsor: Pliant Therapeutics Inc
		Protocol Number: PLN-74809-IPF-205

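### The end-of-participation PET/MRI is offered only to participants who choose to withdraw after week 6; other early exits have no scan provided for, and the SAP would normally only list an early scan

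*Protocol*

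**What the plan says.** **Who is offered the scan.** The Synopsis (Study Design), Section 3.1 and Section 12.5.1 of the protocol give the same trigger: "If a participant elects to withdraw from the study after the 6th week of randomization". Only then is a final PET/MRI offered.

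**Other ways out.** Section 11 states: "The Investigator or Sponsor may withdraw a participant from the study or discontinue study drug for any of the following reasons". The reasons include noncompliance, COVID-19, adverse events and laboratory changes. Section 8.8.3 adds: "Withdrawal from the study in the event of a SAE and therapeutic measures taken shall be at the discretion of the Investigator".

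**What happens on leaving.** Section 11 continues: "If a participant is withdrawn from the study or discontinues study drug, they will undergo early termination assessments". In Appendix 1 the PET/MRI row is marked at the pre-baseline visit and at Week 12. The EoS/ET column is blank for that row, as the table reads in the text available.

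**Safety stops of study drug.** Under Section 3.1 these participants "will be encouraged to remain in the study to complete all remaining assessments". Only where staying is impossible does the section fall back on an ET visit, and it mentions no scan there.

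**How the SAP treats the data.** SAP 5.11.1: "The primary endpoint is the change from baseline to week 12 in the top quartile mean SUV for the whole lung". SAP 5.2.7: "Early Termination (ET) assessments will not be summarized unless the ET visit falls on a scheduled visit". SAP 5.2.8 tabulates only scheduled post-baseline values unless stated otherwise. SAP 5.1.5 admits a participant to the PD population with a baseline result and any one post-baseline PET/MRI or PD result, without fixing when the scan was done.

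**The concern.** A change in SUV cannot be computed without a post-baseline scan, and Section 7.14 of the protocol rules out imputation. The offer depends on who made the decision to leave. Take two participants who leave at Week 10, neither yet scanned. The one who chooses to go is offered a scan; for the one removed by the investigator, nothing is provided. The stated purpose of the offer is better data capture, and that purpose applies equally to both.

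The protocol handles an exploratory measure more broadly. Section 7.9 and the footnotes to Appendix 1 call for a PK sample at the ET visit, if possible, whenever a participant leaves early, whatever the reason. The primary outcome has no matching rule.

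With about 12 participants, 4 of them on placebo, each scan carries weight. A scan that was never acquired cannot be recovered later, whereas an analysis rule can still be changed before database lock.

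**Working it through.** **Step 1. Follow each exit route after week 6, for a participant with no post-baseline scan yet.**

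| Route | Scan provided for? | Would it enter the SAP's Week 12 primary analysis? |
|---|---|---|
| Stops drug for safety, stays in study | Yes, the Week 12 scan (3.1, 6.2) | Yes |
| Chooses to withdraw | Yes, offered (Synopsis, 3.1, 12.5.1) | Normally no: listed only (SAP 5.2.7, 5.2.8) |
| Stops for safety, cannot stay, and chooses to withdraw | Can fall under the offer | Normally no |
| Leaves through an ET visit without choosing to withdraw | No provision | No scan to analyse |
| Withdrawn by investigator or sponsor (11, 8.8.3) | No provision | No scan to analyse |

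Before the week-6 limit, no early leaver is offered a scan by any route. In the 7 days before Week 12, a leaver may already have had the Week 12 scan.

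The table shows two separate gaps. The protocol gap is the last two rows. The SAP gap is the second and third rows: the scan exists, but the endpoint is defined at Week 12 and early data are normally only listed.

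**Step 2. Check the stated sample size.** The plan gives about 12 participants at 2:1. 12 × 2/3 = 8 active and 12 × 1/3 = 4 placebo, which agrees with Section 12.2 of the protocol. No effect size, SD, power or dropout rate is given, so there is no power calculation to reproduce.

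**Step 3. Precision cost of one lost scan.** SAP 5.11.1 describes an ANCOVA with baseline and treatment, so 3 parameters, and SAP 5.11 sets 95% intervals. Ignoring chance baseline imbalance, the half-width in residual-SD units is

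t(0.975, n − 3) × √(1/n_active + 1/n_placebo).

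| Active v placebo | √ term | t | Half-width | Change |
|---|---|---|---|---|
| 8 v 4 | 0.612 | 2.262 (9 df) | 1.385 | – |
| 7 v 4 | 0.627 | 2.306 (8 df) | 1.445 | +4.3% |
| 8 v 3 | 0.677 | 2.306 (8 df) | 1.561 | +12.7% |

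The legend under the model code also lists standard-of-care use. With that fourth parameter the half-widths are 1.412, 1.482 (+5.0%) and 1.601 (+13.4%).

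**Step 4. How likely is a loss?** The documents give no rate. Assume each participant has probability q of leaving without a Week 12 scan. The chance of at least one among n is 1 − (1 − q)^n.

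- q = 0.05: 46% among 12 and 19% among the 4 on placebo; expected losses 12 × 0.05 = 0.6.
- q = 0.20: 93% among 12 and 59% among the 4 on placebo; expected losses 12 × 0.20 = 2.4.

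These figures cover every unscanned exit. The protocol gap alone is a subset, so its own probability is lower.

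**The case against.** A reader might infer that anyone who leaves for safety loses the primary outcome. The documents do not support that. Safety discontinuers are first asked to stay and complete assessments (Sections 3.1 and 6.2, repeated for liver and QTc stops in Sections 9 and 10), and those who stay are scanned at Week 12. The reasons in Section 11 may lead only to stopping the drug. The scan offer directly follows the ET sentence in Section 3.1, so someone who cannot continue and chooses to leave can fall under it. Nothing forbids a scan in the other cases.

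A reader might also infer that a voluntary leaver keeps the primary outcome and a removed participant does not. The SAP contradicts this: under 5.2.7, 5.2.8 and 5.11.1 neither would normally have a value in the Week 12 analysis. A protocol edit alone would therefore recover none of the lost precision. This objection stands, and it is why the fix must include the SAP.

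A third inference is that the loss biases the comparison, because adverse-event exits may differ by arm. That is possible, but nothing in the documents shows it, and Sections 1.2 and 3.2 describe favourable tolerability. If the drug did cause such exits, the loss would fall mainly on the active arm, where one scan costs about 4%; the 13% figure needs a placebo loss.

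The blank ET cell is weak evidence alone, since the expressly offered scan is not marked there either. The gap rests on the wording of the trigger read together with Section 11. Finally, Section 12.1 says no hypotheses are tested, and some participants removed for an adverse event might not be fit for a scan. Both points limit the size of the concern but do not close the gap.

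**Conclusion.** The concern holds in a narrow form. The end-of-participation scan is provided for only when the participant chooses to withdraw after week 6. For an unscanned participant removed after week 6 by the investigator or sponsor, or leaving through an ET visit without choosing to withdraw, the protocol provides no post-baseline scan. Separately, the SAP leaves early scans without a defined use in the primary analysis, although its PD population would accept them.

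The illustrative size is a 95% interval about 4% wider for one lost active scan and about 13% wider for one lost placebo scan. This assumes one such exit, the two-term ANCOVA and balanced baselines. The documents support no estimate of how often it would happen, nor of any bias. The point is worth acting on because the change is small and a missing scan is permanent.

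**What to change.** 1. **Protocol.** In the Synopsis, Section 3.1 and Section 12.5.1, offer the scan to any participant who leaves the study after week 6, for any reason, without a post-baseline scan. Make it subject to the participant's agreement and the investigator's view that a scan is appropriate. Add a conditional PET/MRI entry with a footnote to the ET column of Appendix 1, as already exists for PK.
2. **SAP, before database lock.** State that early end-of-participation scans enter a prespecified analysis of the primary endpoint, exempt from 5.2.7 and 5.2.8. One option is a sensitivity ANCOVA using the last post-baseline scan, with the study day of each scan listed. The Week 12 analysis can stay as the main one.
3. **Consistency.** Section 11 sends anyone who discontinues study drug to ET assessments, while Section 3.1 asks safety discontinuers to remain and complete all assessments. The two must be reconciled so that sites know which visits, and so which scan, apply.

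**Cost.** Some protocol wording, one schedule footnote and one further SAP analysis. The early scan replaces the Week 12 scan, so the total stays at two scans and within 2 × 11 = 22 mSv (Section 7.10.1). The main drawback is interpretive: an early scan reflects less than 12 weeks of treatment, which is why a sensitivity analysis suits it.
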